9.4.3 Analysis of the Exploratory Outcomes

ANCOVA will be also used to examine the diet effect on the other exploratory outcomes, where each outcome measure over time will be used as a dependent variable with age and the outcome at day 1 as covariates.

Longitudinal analysis methods, such as repeated measures ANCOVA, random coefficient model or mixed model, will be used to examine the change in the exploratory outcomes over the six days. Within-subject

Abbreviated Title: Tolerability and efficacy of ketogenic diet in Parkinson's Disease

Version Date: 04/19/2021

(mixed model) and across-subject (spearman or Pearson) correlation analysis will be applied to evaluate the relationship between outcome variables.

9.4.4 Safety Analyses

N/A

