Abbreviated Title: Tolerability and efficacy of ketogenic diet in Parkinson's Disease**Version Date:** 04/19/2021

POG glc checks		X	X	X	X	X	X	X	
Beta-OHB level twice daily, except once on day 7****		X	X	X	X	X	X	X	X**** *
Procedures	Screening	Day 1	Day 2	Day 3	Day 4	Day 5	Day 6	Day 7 / Post	W 3 (post)
Plasma dopamine twice daily		X	X	X					
Continuous glucose monitoring (Precision Libre Pro)		X	X	X	X	X	X	X	
n-back working memory test daily (exploratory outcome)		X	X	X	X	X	X	X	X
Stroop word color interference test daily (exploratory outcome)		X	X	X	X	X	X	X	X
MN and PQ keyboard tasks		X	X	X	X	X	X	X	X
Safety monitor (telephone interview) survey 2-4 weeks post-study completion									X
Depression screening tool: Geriatric Depression Scale (GDS)	X							X	X
Gastrointestinal motility / symptoms diary (daily days 1-7)		X	X	X	X	X	X	X	

Abbreviated Title: Tolerability and efficacy of ketogenic diet in Parkinson’s Disease

Version Date: 04/19/2021

Gastrointestinal Symptom Rating Scale	X	X						X	X
Exit Survey acceptability of ketogenic diet									X
Tracking diet via unscheduled calls*****	X								X
*No Day 0 (7 days of baseline diet and history, then Day 1 is first day of admission) **women of childbearing potential ***repeat BMP and magnesium on days 6 and 7 if abnormal in prior days ****check beta-OHB in fasted state at week 3 visit ***** To occur during week between screening visit/enrollment and day 1 of admission and during 2 weeks after day 7. See Section 4.1 for details.									

Abbreviated Title: Tolerability and efficacy of ketogenic diet in Parkinson's Disease

Version Date: 04/19/2021

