4. STUDY DESIGN

4.1 OVERALL DESIGN

The experiment will take place predominantly in the Metabolic Unit, 7SW-S (1-week inpatient) and at home (2 weeks outpatient). Additionally, EEG, TUG, and heart rate variability tests will be performed in the HMCS labs within the 7SW-Neurotesting area.

This study is a single center (NIH Clinical Center), phase 1 feasibility/tolerability assessment of MCT oil subtype of ketogenic diet in a PD cohort, randomized, double-blinded vs. standard American (high-carbohydrate) diet based on macronutrient percentages of calculated daily energy expenditure using measured pCO₂ and pO₂ and Weir formula for indirect calorimetry, performed on screening visit, to give caloric macronutrient ratios 50-55% carb, 35% lipid, 10-15% protein in SAD group and 5-10% carb, 80% lipid, 10-15% protein in MCT-KD group on the 7SW-S Metabolic Unit with assistance of CC Nutrition Department staff. Consent, baseline lipid panel, BMP, and pregnancy test will be done at screening visit. Randomization will occur upon screening visit, stratified by age ≥ 65 or < 65 and baseline TUG score ≥ 11.5 s or < 11.5 s. Protein macronutrient percentage of individual calculated daily energy intake will be the same between the two groups. Diet will be within subject factor for both groups, as pre-diet intervention baseline testing is planned for hospital day #1. The potential confound of changes in activity/exercise level while in the hospital on physiologic and clinical outcomes is recognized. To address this, study investigators will form an individualized exercise plan incorporating baseline exercise and activity levels to involve stationary bike at target HR based on age-adjusted HR max target using Tanaka's formula validated in the elderly population, $208 - 0.7 \times \text{age}$, in order to approximate each participant's daily baseline intensity levels from questionnaires.

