Abbreviated Title: Tolerability and efficacy of ketogenic diet in Parkinson's Disease

Version Date: 04/19/2021

often to prescribe the diet for a period of time such as 6 months or 1 year because the therapeutic benefit of seizure reduction/cessation often endures long after switching back to a regular diet, such data are not available for Parkinson's and will require further study, which this study does not attempt to address. Rather, this study proposes to address what level of ketosis can be achieved through an MCT oil supplemented, monitored diet with less stringent carbohydrate restriction and therefore presumably better tolerated as a long-term therapy; whether there may be particular biomarkers to indicate success of the diet, such as EEG central beta power, heart rate variability or BDNF; if side effects of MCT oil are tolerable in this population with known gastro-intestinal paresis; and what effect does a given ketosis value have compared to another on serially repeated, validated measurements in PD.

Anecdotally, PwP adhering to ketogenic diet or other low-carbohydrate diets such as Paleolithic diet have reported that both diets, avoiding carbohydrate and large amounts of protein, improve symptoms such as walking speed, tremor and fatigue, even at low or undetectable values of ketosis as measured from a ketone meter reagent strips, a validated method for beta-OHB levels 0.1 – 6.0 mM (for further details of community engagement please refer to section 5.6). Accordingly, the mechanism underlying benefits of a low carbohydrate diet appears to be more multifaceted than simply ketosis, potentially involving differences related to fatty acid metabolism, levels of PUFA (polyunsaturated fatty acids), glycolysis, insulin sensitivity, levels of antioxidants, DNA repair, and buffers for coenzyme activation. This remaining question drives the study, with the question of “do ketosis values matter,” which is well posed for inpatient metabolic unit study.

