8.4.4 Time Period and Frequency for Event Assessment and Follow-Up

The occurrence of an adverse event (AE) or serious adverse event (SAE) may come to the attention of study personnel during study visits and interviews of a study participant presenting for medical care, or upon review by a study monitor.

Abbreviated Title: Tolerability and efficacy of ketogenic diet in Parkinson's Disease

Version Date: 04/19/2021

All AEs including local and systemic reactions not meeting the criteria for SAEs will be captured on the appropriate case report form (CRF). Information to be collected includes event description, time of onset, clinician's assessment of severity, relationship to study product (assessed only by those with the training and authority to make a diagnosis), and time of resolution/stabilization of the event. All AEs occurring while on study must be documented appropriately regardless of relationship. All AEs will be followed to adequate resolution.

AE will be solicited through daily keto-induction symptom worksheets. Opportunity for unsolicited AE will be provided / encouraged, with instructions for conversation to occur initially with study PI / IMM to maintain blinding of study raters, when AE is not serious and is non-emergent.

Any medical condition that is present at the time that the participant is screened will be considered as baseline and not reported as an AE. However, if the study participant's condition deteriorates at any time during the study, it will be recorded as an AE.

Changes in the severity of an AE will be documented to allow an assessment of the duration of the event at each level of severity to be performed. AEs characterized as intermittent require documentation of onset and duration of each episode.

Study PI will communicate to IMM and record all reportable events with start dates occurring any time after informed consent is obtained until 7 (for non-serious AEs) or 30 days (for SAEs) after the last day of study participation. Study AI will also be involved in evaluation after study completion when non-emergent. Events will be followed for outcome information until resolution or stabilization.

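### Safety analysis is set to N/A although tolerability of MCT oil is a study question, and the cutoff for non-serious adverse events is not reconciled with the later safety call

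*Combined protocol and SAP*

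**What the plan says.** **Analysis.** Under "9.4.4 Safety Analyses" the entry is N/A. Section 9.3 defines no safety set and only states that 32 subjects are randomised; the table of contents still lists a toxicity-evaluable population. Section 9.4.3 applies ANCOVA and longitudinal models to the exploratory outcomes. Section 3 includes keto-induction symptoms and GSRS among these.

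**Purpose.** Section 4.1 describes a "phase 1 feasibility/tolerability assessment of MCT oil subtype of ketogenic diet in a PD cohort". Section 4.2 lists, among the questions the study addresses, "if side effects of MCT oil are tolerable in this population with known gastro-intestinal paresis".

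**Data collected.** Section 8.4.4 puts all non-serious adverse events on the case report form with severity and relationship. The Schedule of Activities has electrolytes, a daily gastrointestinal diary and GSRS.

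**Time window.** Section 8.4.4 has the investigator "record all reportable events with start dates occurring any time after informed consent is obtained" and "until 7 (for non-serious AEs) or 30 days (for SAEs) after the last day of study participation". The Schedule of Activities lists "Safety monitor (telephone interview) survey 2-4 weeks post-study completion". Section 7.2 also places a safety telephone contact at about 2-4 weeks, but counts from the last dose and says the contact is made before the participant is removed from the study.

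**The concern.** A phase 1 trial of a supplement that the protocol says has not been studied in Parkinson's disease asks whether its side effects are tolerable, records adverse events in two randomised arms, and then states that no safety analysis applies. Followed literally, the adverse event forms yield no prespecified comparison by arm and no denominator.

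The denominator matters. Section 6.1.1 excludes from statistical analysis the data of a participant who is unblinded for a serious adverse event and stays in the study. Section 6.3 provides for withdrawal after a major adverse event unless there is agreement to continue. Without a safety set, the participants who tolerate the diet worst can be missing from the only analyses that touch tolerability.

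On timing, a call meant to detect late problems is of limited use if a non-serious event it finds started too late to be recordable.

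**Working it through.** The plan states no safety figure to reproduce. The check compares sections, counts days and looks at precision.

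**1. What has a planned analysis by arm**

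| Item | Planned analysis |
|---|---|
| Keto-induction symptom scores | Yes: synopsis, sections 3 and 9.1, analysed under 9.4.3 |
| GSRS | Yes, through section 3 and 9.4.3, although the outcome list in 9.1 omits it |
| Daily gastrointestinal diary | Not listed as an outcome in section 3 or 9.1 |
| Adverse event incidence, severity, relationship | None |
| Electrolyte abnormalities | None |
| Withdrawals for adverse events | None |

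**2. Where a randomised diet contrast exists.** Diets start on hospital day 2. After discharge both groups take the ketogenic diet. Days 2-7 are therefore the only period in which the arms differ in current diet. At home they differ only in prior ketogenic exposure.

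**3. Day counts.** Take the week-3 visit as day 0 and as the end of participation, in line with the three-week participant duration in the synopsis.

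- Non-serious cutoff: start date by day 7. Serious cutoff: day 30.
- Call, Schedule of Activities: days 14 to 28.
- Call minus non-serious cutoff: 14 - 7 = 7 days, to 28 - 7 = 21 days.
- Serious cutoff minus call: 30 - 28 = 2 days, to 30 - 14 = 16 days. The serious window therefore covers the call.
- A non-serious event starting from day 8 up to the call falls outside the rule. One starting by day 7 can still be recorded at the call, because the limit is on the start date.
- Under 7.2 the clock starts at the last dose. Section 7.1 lets a participant stop the diet and stay in the study. For someone who stops at discharge, two weeks before the week-3 visit, the call falls at -14 + 14 = day 0 to -14 + 28 = day 14. The two anchors give different answers.

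**4. Precision with 16 per arm.** Section 2.3.1 cites a placebo-controlled Alzheimer's trial of an MCT powder: GI events 49% versus 27%, diarrhoea 24% versus 14%. Used only for illustration:

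- Expected participants with a GI event: 0.49 × 16 = 7.8 and 0.27 × 16 = 4.3.
- Power, two-sided 5%, normal approximation with p̄ = (0.49 + 0.27)/2 = 0.38. Pooled SE = √(2 × 0.38 × 0.62/16) = 0.1716. Unpooled SE = √((0.49 × 0.51 + 0.27 × 0.73)/16) = 0.1671. Power = Φ((0.22 - 1.96 × 0.1716)/0.1671) = Φ(-0.70) = 0.24.
- The same calculation for diarrhoea gives 0.11.
- Exact (Clopper-Pearson) 95% interval for 8/16: 25% to 75%.
- If an event type is seen in 0 of 32, the one-sided 95% upper limit is 1 - 0.05^(1/32) = 8.9%.

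These figures support estimates with intervals, not a hypothesis test.

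**The case against.** **Tolerability is not ignored.** Adverse events are solicited through the daily keto-induction worksheets, and those symptoms and GSRS already have a randomised comparison under 9.4.3. This stands. A reader might infer from the N/A that the trial reports nothing on tolerability, or that this is the one question with a randomised control. The documents support neither: the symptom scales are analysed, and Timed Up & Go on day 7 shares the same control. A GSRS ANCOVA need not be added. What remains is that an ANCOVA on scale scores does not give incidence, severity, relationship or withdrawals.

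**The primary composite touches tolerability.** It requires retention above 80% and participant acceptability, and Table 1 in section 2.1 reports attrition alongside side effects. This also stands, but neither criterion counts adverse events or compares arms.

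**The timing gap depends on a definition.** The end of participation is undefined. Because 7.2 places the call before removal from the study, the call could itself be the last day, and then there is no gap. The three-week duration and the schedule's placing of the call after completion favour the other reading. A reader might infer a certain hole in recording; the documents support an ambiguity to be reconciled.

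**Serious events.** A reader might also want the call moved beyond day 30. Nothing makes the call the means of capturing serious events, so an earlier call contradicts nothing.

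**The 49% versus 27% rates may not carry over.** Correct. They come from a different population, product and dose, and the same paragraph reports far fewer GI effects once the mixing base was changed. They serve only to show how little a test could do.

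**Conclusion.** The point holds in limited form. The plan states a tolerability question and collects the adverse event data, but plans no analysis of them by arm and defines no safety set. The uncovered items are adverse event incidence, severity and relationship, electrolyte abnormalities and withdrawals for adverse events.

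Only a descriptive summary is realistic, given about 24% power even at the illustrative GI rates and an interval of 25% to 75% around 8 of 16.

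The recording mismatch is 7 to 21 days and concerns non-serious events starting after day 7. It assumes that participation ends at the week-3 visit. It disappears if the call ends participation, and it changes again if the call is timed from an early last dose. No primary or secondary result changes.

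**What to change.** **Section 9.3.** Define a safety set of everyone who started a study diet, including participants later withdrawn or unblinded, and state that the exclusion in 6.1.1 does not apply to it.

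**Section 9.4.4.** Replace N/A with a descriptive analysis:

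- number and percentage with any adverse event and any GI adverse event, by randomised arm, for days 2-7, with exact 95% confidence intervals;
- severity, relationship, electrolyte abnormalities and withdrawals for adverse events in the same layout;
- home-phase adverse events tabulated separately, by prior ketogenic exposure;
- a statement that no hypothesis test is intended.

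**Sections 1.3, 7.2 and 8.4.4.** Define when participation ends, use one anchor for the safety call, and run the non-serious recording window to that call. The serious event window can stay as it is.

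**Cost.** Protocol and SAP wording, a few tables from data already collected, and a few more events to record. No change to sample size or visits.

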9.4.5 Baseline Descriptive Statistics

Descriptive statistics, such as mean, median, standard deviation, frequency, will be calculated to demonstrate patients' baseline demographics and clinical characteristics

9.4.6 Planned Interim Analyses

We plan to perform one Interim analysis which is scheduled when the primary outcome (TUG) data is collected from 8 patients from each group (mid-way). O'Brien-Fleming approach was used to prespecify efficacy boundary. The bounds are set as $p=0.0054$ ($df=14$, $t\text{-value}=3.287$, or effect size=1.64) and final analysis with bound $p=0.0492$ ($df=26$, $t\text{-value}=2.06$, effect size=0.78).

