9.2 SAMPLE SIZE DETERMINATION

Power analysis was performed based second outcome, TUG score, rather than feasibility outcome due to clinical significance of the former for both mobility and fall risk that is felt to be an important justification for this intervention as a pilot study, whereas feasibility ascertainment does not justify the study but merely indicates lack of existing clinical use of this ketogenic diet protocol.

Abbreviated Title: Tolerability and efficacy of ketogenic diet in Parkinson's Disease

Version Date: 04/19/2021

Considering range of TUG tests reported in Parkinson's Disease off dopaminergic medication of 8-17s (Foreman 2011), mean of 10-15s with SD 2.15-3.7s (Foreman 2011, Brusse 2005, Dal Bello-Haas 2011), and association of 1s increase in TUG time with 5.4% increase in odds of reporting a fall (Nocera 2013), it is suggested that fall rate can be reduced by 20% with a 4s reduction in TUG time, which is therefore considered to be a clinically meaningful difference. Minimal detectable change is reported as 4.85s (Dal Bello-Haas 2011) and 3.5s (Huang 2011).

Based on these studies, the difference of 4.5s between the group means, which was considered as clinically important, and standard deviation (SD) of 4s (or effect size of 1.125) were used for power analysis. A two-sample t-test was applied to estimate sample size by assuming that the primary outcome, TUG, followed normal distributions, and the variances of the two groups were equal. Power analysis indicated that a total of 28 subjects, 14 per group, will be needed to achieve a power of 80% to detect the difference of 4.5s at significant level of 0.0492. The sample size calculation considered one planned interim analysis scheduled to be conducted when 8 subjects per group have completed. Using O'Brien-Fleming approach, the interim analysis will be conducted with bound, $p=0.0054$ ($t\text{-value}=3.287$, $df=16$) and final analysis with bound $p=0.0492$ ($t\text{-value}=2.06$, $df=26$). By anticipating 10% dropout rate, we will need to recruit a total of 32 subjects (16 per group).

Randomization

Stratified randomization method will be used to control the covariates of age (≤ 65 vs. >65) and TUG baseline score (≥ 11.5 s, vs. <11.5 s Nocera 2013). With these two covariates, there are 4 possible block combinations (TUG ≤ 11.5 s & age ≤ 65 , TUG ≤ 11.5 s & age >65 , TUG >11.5 s and age ≤ 65 , TUG >11.5 s & age >65).

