9.4.2 Analysis of Secondary Endpoint

To evaluate the diet effect on the TUG score, analysis of covariance (ANCOVA) will be performed with age and TUG score at day 1 as covariates, and TUG score on day 7 as a dependent variable.

Repeated measures ANCOVA with age as a covariate will also be performed to evaluate the within-subject effect: baseline day 1 vs. day 7 (inpatient) vs. 3 weeks (outpatient) of the intervention, and between subject-effect (diet): ketogenic diet vs. standard American diet.

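### The interim and final bounds for Timed Up & Go (TUG) give an overall two-sided error of about 0.051, section 9.2 gives the wrong interim df, and the t and effect-size forms do not fit the planned ANCOVA

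*Combined protocol and SAP*

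**What the plan says.** Section 9.1 sets a two-sided hypothesis for day-7 TUG. In section 9.2, "A two-sample t-test was applied to estimate sample size", with a difference of 4.5 s and a "standard deviation (SD) of 4s (or effect size of 1.125"). The result is "a total of 28 subjects, 14 per group, will be needed to achieve a power of 80" per cent, "to detect the difference of 4.5s at significant level of 0.0492". A 10% dropout allowance raises 28 to 32.

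For the look at 8 per group, section 9.2 states that "the interim analysis will be conducted with bound, $p=0.0054", and it attaches t=3.287 and df=16. Section 9.4.6 says that an O'Brien-Fleming "approach was used to prespecify efficacy boundary". It repeats p=0.0054 and t=3.287, but with df=14 and an effect size of 1.64. It then adds "and final analysis with bound $p=0.0492", with df=26, t=2.06 and an effect size of 0.78. It describes the look as mid-way.

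For the analysis itself, section 9.4.2 says that "analysis of covariance (ANCOVA) will be performed with age and TUG score at day 1 as covariates". No section states the overall alpha, the information fraction or which form of the bound governs.

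**The concern.** An O'Brien-Fleming pair is meant to hold a stated overall error across both looks. Here the final level is close to 0.05 although some error has already been spent at the interim look, so the sum needs checking. The interim bound also carries two different df. In addition, the t and effect-size cut-offs come from a test that is not the planned analysis.

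These are the only numerical efficacy thresholds in the plan, and they apply to the outcome that sets the sample size. Section 10.2 lists demonstrated efficacy as a possible ground for stopping. The recruitment criterion of the primary feasibility composite (sections 3 and 9.1) allows the target of 32 to be changed by the interim analysis. The bound should therefore have one clear value before any data are seen.

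**Working it through.** **Inputs.** Two-sided test (9.1). Difference 4.5 s, SD 4 s, d=1.125, 14 per group analysed, 32 recruited, interim at 8 per group, p bounds 0.0054 and 0.0492 (9.2, 9.4.6). ANCOVA with two covariates (9.4.2). Assumed: overall two-sided alpha 0.05. The information fraction is taken as 16/28=0.571 (of those analysed) and as 16/32=0.50 (of those recruited).

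**1. The plan's sample size reproduces.** Noncentral t with df=26 and noncentrality 1.125 × √(14/2) = 2.976, tested at 0.0492, gives 81.5% power; 13 per group gives 78.4%. Dropout: 28/0.9 = 31.1, rounded up to 32 (16 per group).

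**2. The forms within 9.4.6 agree.** For a two-sample t-test, df = 2n − 2 and effect size = t × √(2/n).
- Interim: p=0.0054 on 14 df is t=3.287, and 3.287 × √(2/8) = 1.64.
- Final: p=0.0492 on 26 df is t=2.063, and 2.06 × √(2/14) = 0.78. The rounded t=2.06 is p=0.0495.

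**3. The df in 9.2 is wrong.** Eight per group gives 2 × 8 − 2 = 14, not 16. On 16 df, t=3.287 is p=0.0046, and p=0.0054 would need t=3.215.

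**4. Overall error of the pair.** Error = 1 − P(|Z1| < z1 and |Z2| < z2), with correlation √(information fraction), z1=2.782 and z2=1.967.
- Fraction 0.50: 0.0513.
- Fraction 16/28: 0.0508.
- Simulated t-tests at 8 then 14 per group: 0.0513 in one run of 4 million trials (standard error about 0.0001), and about 0.0515 in repeat runs. With the rounded cut-offs 3.287 and 2.06, the first run gives 0.0517.

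The ratio z1/z2 = 1.4145 is √2, the O'Brien-Fleming shape for a half-way look. The shape is right, but the final constant is 1.967 where about 1.977 is needed for 0.05.

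**5. Carry-over to the ANCOVA.** Intercept, diet and two covariates use 4 df, leaving 16 − 4 = 12 and 28 − 4 = 24.
- On 12 df, t=3.287 is p=0.0065; p=0.0054 needs t=3.387.
- On 24 df, t=2.06 is p=0.0504; p=0.0492 needs t=2.072.

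Used as ANCOVA cut-offs, the stated t values are looser than the stated p-values.

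**6. Replacement bounds.** With the interim bound kept at p=0.0054, normal theory gives a final bound of 0.0479 (fraction 0.50) or 0.0484 (16/28). Simulated t-tests at 8 then 14 per group put it near 0.0478.
- 0.0054 with 0.0475: error 0.0496 (0.50) and 0.0492 (16/28) by normal theory; 0.0497 to 0.0499 in simulated t-tests at 8 then 14 per group.
- 0.0052 with 0.0480, the classical half-way pair: 0.0500 and 0.0496 by normal theory, but 0.0501 to 0.0503 in the same simulations.
- Power at 14 per group and final level 0.0475: 81.1%.

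Two further simulations of 0.0054 with 0.0475, one with t-tests at 8 then 16 per group (6 million trials) and one with a two-covariate ANCOVA at 8 then 14 per group (2 million trials), each gave 0.0503. In those settings 0.0475 is level to about 0.0003, not strictly below 0.05.

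**The case against.** The strongest reply is that little here could mislead. TUG is a secondary outcome in a phase 1 pilot whose primary outcome is analysed descriptively. The excess is about 0.1 percentage points against an alpha that the plan never states. The df of 16 looks like a slip, the total number of participants written for the df, and section 9.4.6 already has 14. The bounds are set first as p-values, which apply directly to the ANCOVA diet term, and no section tells the analyst to use t=3.287 or t=2.06 there. Correcting the final p bound affects only results between about 0.048 and 0.0492.

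Most of this stands, and it limits the point. A reader might infer from the two df values that the p, t, df and effect-size versions of the bound generally contradict one another. They do not: within section 9.4.6 they match to rounding, and the only internal conflict is df=16 in section 9.2. A reader might also infer that the p bounds fail under ANCOVA, or that the sample size is wrong. Neither follows: the p bounds can be used as they stand, and 28 and 32 both reproduce.

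The reply does not remove three facts. The pair exceeds 0.05 at both readings of the information fraction. Section 9.2 contains an arithmetic error. The plan does not say which form governs, or which test is used at the interim look.

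**Conclusion.** The point holds in a limited form. With overall two-sided alpha assumed to be 0.05, the stated pair gives 0.0508 to 0.0515, an excess of about 0.1 percentage points. The interim df in section 9.2 is wrong. The t and effect-size cut-offs belong to an unadjusted t-test and do not carry over to the planned ANCOVA. The normal-theory figures rest on the two readings of the information fraction, and the simulated ones on normally distributed data with equal variances. The practical effect is small: only borderline TUG results are touched, and neither the sample size nor the feasibility thresholds change. It should still be corrected, because these are the plan's only efficacy bounds and the correction costs almost nothing.

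**What to change.** In sections 9.2 and 9.4.6:

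- State an overall two-sided alpha of 0.05 and the information fraction: 16/28, or 16/32 if mid-way refers to those recruited.
- Keep the interim bound at p=0.0054 and lower the final bound to p=0.0475, or recompute it for the stated fraction (0.0479 at 0.50, 0.0484 at 16/28 by normal theory). Normal theory is slightly generous at this size, so a recomputed bound is best confirmed by simulating the ANCOVA itself.
- Correct df=16 to df=14 in section 9.2.
- Say that the p-value of the ANCOVA diet term governs at both looks, and label the t, df and effect-size figures as t-test equivalents only, updating the final ones to the new bound.
- Restate power at the new final level: about 81% at 14 per group, so 28 and 32 stand.

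The cost is a change of wording and a slightly stricter final threshold, with power moving from 81.5% to 81.1%. Recruitment and participant procedures are unaffected.
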